## 1. INTRODUCTION AND RATIONALE

### 1.1. Introduction

Gingival recession (GR) is a frequent mucogingival deformity characterized by the apical displacement of the gingival margin with exposure of the root surface beyond the cemento-enamel junction (CEJ) [1–3]. Its prevalence increases with age and may lead to dentin hypersensitivity, root caries, plaque retention, aesthetic impairment, and patient discomfort [4,5]. Among the available treatment modalities, the coronally advanced flap (CAF), particularly when combined with a subepithelial connective tissue graft (SCTG), is a **well-documented and widely adopted approach** for the management of single and multiple recession-type defects, providing predictable root coverage, gain of keratinized tissue, and long-term stability [6–8]. However, CAF + SCTG procedures may still be associated with postoperative morbidity, donor-site discomfort, and incomplete root coverage in some cases [9,10]. Therefore, adjunctive strategies aimed at enhancing wound healing and increasing the probability of complete root coverage (CRC) remain of significant clinical interest.

Hyaluronic acid (HA), a high-molecular-weight, non-sulfated glycosaminoglycan, is a key component of the periodontal extracellular matrix and plays a pivotal role in angiogenesis, cell migration, proliferation, and differentiation during tissue healing [11–13]. HA has been shown to accelerate granulation tissue formation, modulate inflammatory responses, and stimulate fibroblast and keratinocyte activity [14–16]. Preclinical studies demonstrated that HA enhances vascularization, supports osteoinduction, and upregulates osteogenic markers such as Runx2, alkaline phosphatase (ALP), and osteocalcin [17,18]. In vitro studies further confirm that HA promotes fibroblast proliferation, migration, and extracellular matrix synthesis [19,20], while cross-linked formulations prolong its bioactivity in surgical wounds [21]. Moreover, HA exhibits bacteriostatic properties against periodontopathogens such as *Aggregatibacter actinomycetemcomitans* and *Porphyromonas gingivalis* [22], potentially reducing early contamination of surgical sites.

The adjunctive use of HA in periodontal regenerative and mucogingival surgery has been investigated in several clinical studies. Randomized controlled trials (RCTs) demonstrated significantly greater clinical attachment level (CAL) gain, mean root coverage (MRC), and CRC when

HA was used in combination with CAF compared to CAF alone [23,24]. Case series also reported high root coverage percentages and enhanced esthetic outcomes when HA was combined with SCTG in tunnel and minimally invasive techniques [25,26]. Beyond recession coverage, clinical studies on intrabony defects showed that HA, particularly when combined with xenografts, promoted the formation of new bone, cementum, and periodontal ligament [27]. Moreover, HA application has been associated with reduced postoperative pain and improved palatal wound healing in donor sites following free gingival grafting [28]. A recent systematic review and meta-analysis concluded that HA may provide additional clinical benefit in both non-surgical and surgical periodontal therapy, although heterogeneity across studies highlights the need for further high-quality trials [29].

Parallel to clinical findings, mechanistic studies provide biological plausibility for the observed effects. Fibroblasts play a central role in periodontal wound healing through extracellular matrix synthesis, wound contraction, and secretion of growth factors [30]. In vitro investigations demonstrated that HA enhances fibroblast proliferation, stimulates type I and III collagen synthesis, and modulates cytokine and matrix metalloproteinase activity [19,20]. Furthermore, periodontal ligament (PDL) cell and cementoblast studies confirmed that HA supports cell viability and induces the expression of mineralization-related genes [16,31]. Culturing fibroblasts derived from SCTGs obtained in clinical settings offers a unique translational approach, allowing donor-specific responses to HA to be studied under standardized conditions and correlated with clinical outcomes [32,33]. This bench-to-bedside model strengthens the biological rationale for HA-mediated wound healing and regeneration.

Based on this rationale, the present randomized controlled clinical trial was designed to evaluate the potential benefits of adjunctive HA application in CAF combined with SCTG for the treatment of single RT1 and RT2 gingival recession defects. In parallel, an in vitro study using fibroblasts isolated from SCTGs of the same patients will investigate cell proliferation, migration, and expression of wound healing-related genes in the presence or absence of HA. Together, these complementary investigations aim to provide a comprehensive understanding of the clinical and biological effects of HA, potentially paving the way for optimized regenerative protocols in periodontal plastic surgery.

## 1.2. Study Rationale

The rationale for this study is to evaluate whether the adjunctive application of cross-linked hyaluronic acid gel (hyaDENT BG®) enhances clinical outcomes of coronally advanced flap combined with subepithelial connective tissue graft (CAF + SCTG) in single RT1/RT2 gingival recessions. By promoting fibroblast migration, proliferation, and angiogenesis, HA may increase complete root coverage rates, improve patient-reported outcomes, and reduce donor-site morbidity. A parallel in vitro study using fibroblasts from the same patients will explore the cellular and molecular mechanisms underlying the clinical findings, strengthening the biological plausibility of the results.

## **2. STUDY PRODUCT DESCRIPTION**

The investigational product is hyaDENT BG®, a sterile, transparent, highly viscous gel containing highly purified hyaluronic acid of non-animal origin with specifically adjusted molecular weight.

### **2.1 Study Product Description**

The hyaDENT BG® gel (Fig. 1) is a sterile, resorbable, cross-linked hyaluronic acid preparation specifically designed for dental applications. It is primarily used to support soft tissue healing and regeneration, particularly in mucogingival procedures such as coronally advanced flap (CAF) surgery combined with connective tissue grafting. Its biocompatibility and prolonged residence time at the surgical site enable sustained stimulation of fibroblast migration, angiogenesis, and extracellular matrix synthesis, which are critical for optimal wound healing outcomes.

In periodontal plastic surgery, hyaDENT BG® serves as an adjunctive biomaterial to enhance root coverage predictability and keratinized tissue gain, while reducing patient morbidity associated with donor-site harvesting. Evidence supports its clinical efficacy in improving complete root coverage, reducing postoperative pain and edema, and accelerating the healing process. In addition, its bacteriostatic properties may limit early microbial colonization of the surgical wound.

The product is supplied as a ready-to-use 1.2 ml glass cartridge, containing a transparent, highly viscous gel with the following composition per 1 ml:

- 16 mg cross-linked hyaluronic acid
- 2 mg natural hyaluronic acid
- 6.9 mg sodium chloride
- Water for injection up to 1.0 ml

**Fig 1:** hyaDENT BG®

#### **Manufacturer:**

BioScience GmbH

[name]

[www.bio-science.org](http://www.bio-science.org)

BioScience GmbH is a leading manufacturer specializing in the development and production of medical devices based on hyaluronic acid. All manufacturing activities are carried out under a rigorous Quality Management System, certified according to ISO 13485, ISO 10993, and in compliance with European Medical Device Regulation (MDR). The product is CE-marked (CE 2797), reflecting its adherence to the highest quality and regulatory standards.

#### **Characteristics:**

hyaDENT BG® is a cross-linked hyaluronic acid gel produced through a proprietary stabilization process that ensures a prolonged residence time in the surgical site while maintaining the biological activity of native HA. This cross-linking technology provides controlled, slow degradation, allowing sustained bioactivity during the critical phases of wound healing.

The product exhibits excellent biocompatibility and tissue integration, forming a viscoelastic scaffold that supports fibroblast migration, angiogenesis, and collagen deposition. Its rheological

properties ensure that the gel remains localized at the application site, offering mechanical stability and protection of the underlying graft or connective tissue during the early healing phase.

Additionally, hyaDENT BG® exerts a bacteriostatic effect against common periodontal pathogens and modulates the inflammatory response, contributing to a favorable environment for regeneration. Its hydrophilic and hygroscopic nature facilitates moisture retention and enhances cell–matrix interactions, guiding orderly tissue regeneration and reducing the risk of scar tissue formation.

The study product will be used for its indication. hyaDENT BG® is a sterile medical device intended for single use. When applied in the following dental fields, hyaDENT BG® supports wound healing:

- In the treatment of gingival recession using the coronally advanced flap technique.
- After tooth extraction, due to its positive effect on postoperative swelling, pain, and trismus.
- In the context of aesthetic dentistry, hyaDENT BG®, when injected into a receded interdental papilla, provides a regenerative effect.

#### **Contraindications:**

hyaDENT BG® must not be used in patients with:

- Autoimmune diseases or those undergoing immunotherapy
- Known hypersensitivity to hyaluronic acid
- Severe allergy predisposition
- Acute inflammatory or infectious processes
- Coagulation disorders or patients undergoing anticoagulant therapy
- Hormonal disorders

There are no clinical data regarding the use of this product in pregnant or breastfeeding women, or in adolescents under 18 years of age.

#### **Adverse Events:**

The use of hyaDENT BG® may, in very rare cases, lead to tissue reactions. As with any similar procedure, the use of hyaDENT BG® carries an inherent risk of infection.

During papilla reconstruction, temporary pressure pain may occur as a result of the injection. No interactions of hyaDENT BG® with other medications are known.

## **2.1. Product Registration Status**

All articles used in this clinical trial are CE marked.

## **2.2. Instruction for Use, Handling, Labelling Packaging Type, Contents and Storage**

### **2.2.1. Instruction for Use**

Remove the glass cartridge from the blister and insert it into a cartridge syringe. For application of the product to the treatment area, blunt needles (23G) are recommended. For papilla reconstruction, sharp needles (27G) are recommended. The product is completely degraded over time.

### **2.2.2. Handling**

REGEDENT AG will provide the study site with the required number of hyaDENT BG® cartridges for use exclusively in patients enrolled in the study and strictly according to the approved protocol. Each unit is supplied as a single-use, sterile 1.2 ml glass cartridge packaged in a sealed blister.

The product must not be used if the sterile packaging is opened or damaged prior to use. In such cases, the cartridge shall be discarded following institutional biohazard procedures or returned to the manufacturer for documentation. hyaDENT BG® is intended for single use only and must not be re-sterilized or reused, as reuse may pose a risk of patient infection.

Before application, the glass cartridge is inserted into a compatible cartridge syringe. For application to the recipient site, blunt cannulas (23G) are recommended to deliver the gel directly into the surgical area. In the test group, immediately after harvesting, the subepithelial connective tissue graft is fully soaked in sterile hyaluronic acid gel prior to its placement at the recipient site, as described in detail in Section 7.4 (Surgical procedure). hyaDENT BG® is applied immediately after flap elevation and prior to suturing, ensuring direct contact with the connective tissue graft and the recipient bed.

The gel should be dispensed slowly to achieve an even distribution, creating a thin, homogeneous layer covering the graft. Once applied, the flap is coronally advanced and sutured to ensure complete coverage of the treated site, minimizing the risk of contamination and optimizing healing.

### **2.2.3. Labelling**

The study product is not relabeled specifically for use in this clinical study, since it is a product already available in the market.

### **2.2.5. Storage**

Do not freeze and do not expose to extreme heat. Store at room temperature (2 °C – 25 °C).

### **2.2.6. Important Information**

The scale on the glass cartridge serves as a guide for the user and refers to the final volume. It is not intended for measurement purposes but merely indicates the amount used relative to the nominal content of 1.2 ml.

## **2.3. Device Accountability**

The Investigator must maintain an accurate and up-to-date accountability record of all hyaDENT BG® cartridges received, used, discarded (opened but unused), and returned throughout the duration of the study. This information shall be documented in the Study Product Accountability Log, including product name, lot number, expiration date, date of use, and patient identification code.

At each monitoring visit, the study monitor will verify the completeness and accuracy of the accountability records and cross-check them with source documentation. At study close-out, the monitor or designated delegate will ensure full reconciliation of all investigational product units, confirming that all cartridges have been either used, appropriately discarded, or returned to the sponsor according to Good Clinical Practice (GCP) requirements

#### **2.4. Return of Study Product**

After treatment of the last enrolled patient, any remaining unopened hyaDENT BG® cartridges at the study site must be returned to REGEDENT AG. The sponsor will issue an acknowledgement of receipt, which must be filed in the Investigator Site File (ISF) as part of the essential study documentation.

### **3. RISKS AND BENEFITS OF THE STUDY PRODUCT AND CLINICAL STUDY**

According to the hyaDENT BG® Clinical Evaluation Report (CER) and post-market clinical follow-up (PMCF) data, the product has demonstrated a favorable safety profile and proven performance for its intended use in periodontal and mucogingival procedures. Reported adverse events are rare and limited to mild, transient local reactions such as temporary pressure pain or localized swelling, with no serious device-related events documented.

There are no new or unforeseen risks identified that require additional clinical assessment. The overall risk–benefit ratio remains highly favorable, and the residual risk acceptability, as documented in the Risk Management Report (RMR), is unchanged.

The potential benefits of adjunctive hyaDENT BG® include increased probability of complete root coverage, enhanced soft tissue healing, reduced postoperative discomfort, and decreased donor-site morbidity, which outweigh the minimal associated risks.

### 3.1. Risks Linked to the Product

Risk management for hyaDENT BG® is conducted in accordance with ISO 14971. A comprehensive description of the risk analysis, identified hazards, and control measures is presented in the Risk Management Report (RMR) provided by the manufacturer.

For both the investigational and control interventions, residual and overall risks are considered acceptable, and no additional risks were identified that would require further clinical investigation. Residual risks cannot be further mitigated by the manufacturer; additional risk reduction relies on proper handling and clinical use by trained dental professionals. Therefore, the product must be used exclusively by well-trained clinicians and strictly following the Instructions for Use (IFU).

Relevant side effects identified in the risk analysis and IFU include:

- Allergy or hypersensitivity to hyaluronic acid or excipients
- Localized edema
- Hematoma or transient swelling
- Gingival irritation or inflammation
- Postoperative pain or discomfort
- Localized or systemic infection
- Esthetic dissatisfaction due to partial root coverage
- Delayed healing at donor site (if SCTG used)
- Transient sensory alterations (paresthesia/dysesthesia)

Except for allergic or hypersensitivity reactions to hyaluronic acid, these potential adverse events are considered inherent to mucogingival surgical procedures and may occur regardless of whether hyaDENT BG® is used.

All identified residual risks have been minimized to the lowest achievable level and are considered acceptable when weighed against the expected clinical benefits, in accordance with Essential Requirement 6 of the Medical Device Directive (MDD) 93/42/EEC and MDR requirements.

To further mitigate risks, all investigators will receive training in the correct handling and application of hyaDENT BG® prior to the initiation of the study.

Alternatives to the use of hyaDENT BG® include:

- Standard CAF + SCTG procedure without adjunctive material
- Other soft tissue substitutes or biomaterials
- No surgical treatment (maintaining the recession defect)

### 3.2. Risks Linked to the Study

This clinical investigation is conducted as part of the ongoing **Post-Market Clinical Follow-Up (PMCF)** activities for hyaDENT BG®, designed to detect any previously unreported risks and to further confirm the clinical performance and safety profile documented in the Risk Management Report (RMR).

The investigational product will be applied in conjunction with the **coronally advanced flap and subepithelial connective tissue graft (CAF + SCTG)** technique, which represents a standard and well-documented surgical procedure in periodontal plastic surgery. Therefore, no additional clinical risks are anticipated beyond those normally associated with routine mucogingival surgery.

Compared to current practice, the only specificities introduced by this study are the **patient selection criteria** (inclusion/exclusion), standardized **follow-up schedule**, and additional **data collection procedures** (photographs, questionnaires, and in vitro cell analyses). These activities pose minimal risk to participants and are not expected to have any negative impact on patient safety.

### 3.3. Benefits

Patients participating in this study may benefit from adjunctive application of hyaDENT BG® during CAF + SCTG surgery for the treatment of single RT1/RT2 gingival recessions. The use of cross-linked hyaluronic acid has the potential to enhance soft tissue healing, increase the probability of complete root coverage, and reduce donor-site morbidity by accelerating wound healing and minimizing postoperative pain and swelling.

By improving the quality and stability of the soft tissue seal around teeth, this approach may contribute to better plaque control, reduced gingival inflammation, and improved long-term periodontal stability. Enhanced aesthetic outcomes and greater patient satisfaction are also expected.

Taken together, these data support a favorable benefit–risk ratio for the use of hyaDENT BG® as an adjunct in CAF + SCTG procedures for the proposed clinical indication.

## 4. OBJECTIVES

### 4.1. Primary Objectives

- Complete Root Coverage (CRC) at 12 months (proportion of sites with RD = 0).

### 4.2. Secondary Objectives

- **Mean Root Coverage (MRC)** – percentage of root coverage achieved at 12 months.
- **Recession Reduction (RecRed)** – reduction in gingival recession depth (mm) from baseline to follow-up.
- **Clinical Attachment Level (CAL) gain** – improvement in CAL (mm) from baseline to 12 months.
- **Probing Depth (PD) reduction** – decrease in PD (mm) from baseline to 12 months.
- **Keratinized Tissue Width (KT) gain** - increase in the width of keratinized gingiva (mm) from baseline to follow-up.
- **Operative and postoperative factors** – total procedure time (minutes) and postoperative morbidity, evaluated via Visual Analog Scale (**VAS**) scores for pain and discomfort and by tracking analgesic use in the first week.
- **Early wound healing** – Early Wound Healing Score (EHS) at early time points (3 days, 14 days, 6 weeks) to assess initial healing quality.
- **Esthetic outcome** – Root Coverage Esthetic Score (**RES**) at 12 months to appraise the esthetic success of root coverage.

Periodontal health indices (FMPS, FMBS, BOP) will be monitored throughout the study to ensure consistent oral hygiene and periodontal stability. These variables are not subject to formal hypothesis testing.

### 4.3. Safety Objectives

This study aims to confirm the safety profile of hyaDENT BG® when used as an adjunct to coronally advanced flap combined with subepithelial connective tissue graft (CAF + SCTG).

Through continuous adverse event (AE) and serious adverse event (SAE) monitoring, the study seeks to:

- Identify any previously unknown or unexpected side effects and continuously monitor those already documented in the Instructions for Use (IFU).
- Analyse emerging risks using factual clinical data to enable timely intervention and risk mitigation.
- Detect any potential systematic misuse or off-label application of hyaDENT BG®, allowing for corrective measures or additional training if required.

By systematically documenting and reviewing adverse events throughout the trial, this study ensures the ongoing verification of product safety and contributes to the overall post-market clinical follow-up (PMCF) activities of the manufacturer.

By closely monitoring adverse events and analysing emerging risks, we are committed to ensuring the ongoing safety and efficacy of the device.

#### 4.4. Hypotheses in both the clinical and the in vitro sections

##### 4.4.1. Clinical trial

###### Primary Hypothesis/Alternative Hypothesis (H1)

**H1:** Adjunctive application of hyaDENT BG® during CAF + SCTG surgery results in a higher proportion of sites achieving complete root coverage (CRC) at 12 months compared to CAF + SCTG alone.

###### Secondary Hypotheses (H2-H9)

**H2:** Adjunctive hyaDENT BG® leads to greater mean root coverage (MRC) and greater recession reduction (RecRed) at 12 months versus control.

**H3:** Adjunctive hyaDENT BG® yields greater CAL gain and PD reduction compared to control sites at 12 months.

**H4:** Adjunctive hyaDENT BG® results in greater height of keratinized tissue (HKT) gain compared to CAF + SCTG alone.

**H5:** Patients receiving hyaDENT BG® report lower postoperative pain, swelling, and discomfort (VAS)

**H6:** Adjunctive hyaDENT BG® improves oral health–related quality of life, as measured by the OHIP-14 questionnaire at early postoperative time points (3, 5, 14 days, 6 weeks).

**H7:** Adjunctive hyaDENT BG® improves early wound healing score (EHS) at 3, 5, 14 days, and 6 weeks compared to control.

**H8:** Adjunctive hyaDENT BG® provides better aesthetic outcomes (Root Coverage Esthetic Score, RES) compared to CAF + SCTG alone.

**H9:** Adjunctive hyaDENT BG® is associated with a lower incidence of surgical complications (e.g., flap dehiscence, infection, graft necrosis).

Null Hypothesis (H0): No statistically significant differences are observed between test and control groups in any of the evaluated outcomes

Multiplicity Control: To manage the risk of Type I error across multiple endpoints, a hierarchical testing strategy will be applied to the following prioritized hypotheses: H2 (MRC), H3 (CAL and PPD), H4 (HKT), H5 (VAS), and H8 (RES). Each hypothesis in this sequence will be tested at the  $\alpha = 0.05$  level, and testing will proceed only if the previous hypothesis in the hierarchy is statistically significant. Remaining secondary outcomes (H6, H7, H9) will be analyzed descriptively.

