#### 5.1.1.2 Secondary Endpoints

- **Mean Root Coverage (MRC) and Recession Reduction (RecRed)** at 12 months (T7), expressed in millimeters and as a percentage of baseline RD.
- **Clinical Attachment Level (CAL) gain and Probing Depth (PD) reduction** from baseline (T0) to 12 months (T7).
- **Height of Keratinized Tissue (HKT) gain**, measured from the gingival margin to the mucogingival junction (MGJ) at T4 (12 weeks), T5 (6 months), T6 (9 months), and T7 (12 months).
- Periodontal parameters: **Full-Mouth Plaque Score (FMPS), Full-Mouth Bleeding Score (FMBS), and Bleeding on Probing (BOP)** at T4, T5, T6, T7 to evaluate maintenance of periodontal health.
- **Patient-Reported Outcomes (PROMs):**
  - Visual Analog Scale (VAS) for pain, swelling, and discomfort at T1 (3 days), T2 (14 days), and T3 (6 weeks).
  - Oral Health Impact Profile-14 (OHIP-14) questionnaire at the same time points to assess oral health-related quality of life.
  - Number of analgesics and days of medication recorded at T1.
- **Early Wound Healing Score (EHS):** assessed at T1 (3 days), T2 (14 days), and T3 (6 weeks) to monitor soft tissue healing dynamics.
- **Surgical and postoperative complications:** any intraoperative or postoperative complications (e.g., flap dehiscence, graft necrosis, infection) will be recorded in the adverse event log, including clinical management and outcome.
- **Aesthetic outcomes:** standardized intra-oral photographs will be analyzed to calculate the Root Coverage Esthetic Score (RES) at T7 (12 months) using fixed camera-to-subject distance, identical lighting conditions, and reference positioning. **At T7 (12 months), the esthetic outcome will be assessed using the Root Coverage Esthetic Score (RES), as described by Cairo et al. 2009 [34].**
  - The RES system evaluates five parameters:
    - **Gingival margin (GM):** 0 points = failure of root coverage (gingival margin apical or equal to baseline recession), 3 points = partial root coverage, and 6 points = complete root coverage (CRC).
    - **Marginal tissue contour (MTC):** 0 = irregular/flat margin, 1 = scalloped, physiologic contour.
    - **Soft tissue texture (STT):** 0 = scar formation or keloid-like surface, 1 = normal texture without scarring.

- **Mucogingival junction (MGJ) alignment:** 0 = misaligned MGJ, 1 = MGJ aligned with adjacent teeth.
  - **Gingival color (GC):** 0 = color mismatch with adjacent gingiva, 1 = normal, harmonious color.

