### 5.2.3. Sample Size

This randomized, controlled PMCF study will enroll a total of 34 patients, allocated 1:1 to:

- **Test group (n = 17):** CAF + SCTG with adjunctive hyaDENT BG®
- **Control group (n = 17):** CAF + SCTG without hyaDENT BG®

The slight increase from the initially planned 30 patients is intended to accommodate an approximate 10% drop-out rate, ensuring that about 30 patients (15 per group) complete the study as evaluable. The sample size calculation remains based on the primary endpoint (CRC at 12 months) with 30 evaluable patients, while the additional 4 subjects provide a margin of safety for potential losses to follow-up.

The sample size was determined to reliably detect a clinically meaningful difference in the primary outcome. Previous randomized studies (e.g. Pilloni et al. 2019) have reported CRC rates of roughly 80% with CAF+HA versus 33% with CAF alone, an absolute difference of ~47 percentage points. Using this large effect size (47 pp), a two-sided  $\alpha = 0.05$ , and power ( $1-\beta$ ) of 80%, a minimum of 15 patients per group was deemed sufficient to demonstrate a statistically significant difference in CRC. By enrolling 17 per group (34 total), the study preserves this power assumption while accounting for possible drop-outs, thereby maintaining at least 15 analyzable subjects in each arm.

**Sensitivity Analysis of Power:** The sample size is powered to detect a large CRC difference (47 pp), based on prior data. However, if the true effect is smaller (e.g. 20–30 pp), the study may be underpowered to reach statistical significance. This highlights a potential risk of type II error for modest but clinically relevant differences. Exact power estimates for these scenarios will be calculated by the statistician using final parameters. Overall, the sample size represents a practical balance between feasibility and detecting a meaningful effect

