outcomes while controlling the overall Type I error. In practice, this means the analysis will formally test secondary outcomes in a prioritized sequence, enabling the trial to make stronger evidence-based claims about secondary benefits (e.g., improvements in mean root coverage or patient-reported pain) if the data support them. By pre-specifying this hierarchy, the study design addresses multiplicity and increases the reliability of conclusions drawn from secondary analyses.

Overall, the chosen design – including stratified randomization, an adequate sample with drop-out accommodation, and a controlled approach to multiple endpoints – is intended to ensure that the findings are both scientifically robust and applicable to real-world clinical practice. The results of this study will provide valuable clinical data on the potential benefits of adjunctive hyaDENT BG® in periodontal surgery, which can be compared against published outcomes in the literature and used to guide evidence-based decision-making in periodontal therapy.

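### The secondary testing sequence starts at H2 without a gate on the primary hypothesis H1, so the claimed control of overall Type I error is not guaranteed

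*Protocol*

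**What the plan says.** Section 4.4.1 states the primary hypothesis separately: adjunctive HA "results in a higher proportion of sites achieving complete root coverage (CRC) at 12 months compared to CAF + SCTG alone". Its significance level appears in the sample size section (5.2.3): "Using this large effect size (47 pp), a two-sided $\alpha = 0.05$ , and power".

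The Multiplicity Control paragraph under the secondary hypotheses then applies a testing sequence to the "following prioritized hypotheses: H2 (MRC), H3 (CAL and PPD), H4 (HKT), H5 (VAS), and H8 (RES"). On the level it says "Each hypothesis in this sequence will be tested at the $\alpha = 0.05$ level", and on the gate, "testing will proceed only if the previous hypothesis in the hierarchy is statistically significant". H6, H7 and H9 are descriptive. Nothing in the protocol makes H2 conditional on H1.

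Section 5.5 says that the hierarchy allows a confirmatory reading of the most relevant secondary "outcomes while controlling the overall Type I error".

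On the content of the steps:

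- **H2** as a hypothesis says that HA "leads to greater mean root coverage (MRC) and greater recession reduction (RecRed) at 12 months versus control", but the hierarchy label names MRC only.
- **H3** names two endpoints in the hierarchy itself, CAL and probing depth.
- **H4** (HKT) fixes no time point. Section 5.1.1.2 lists four: 12 weeks and 6, 9 and 12 months.
- **H5** (VAS) draws on this schedule in section 5.1.1.2: "Visual Analog Scale (VAS) for pain, swelling, and discomfort at T1 (3 days), T2 (14 days), and T3 (6 weeks"). Section 7.6.8 gives the VAS questionnaire at 1 week, which is none of those visits.
- **H8** (RES) is one total score at 12 months and raises no question here.

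**The concern.** A fixed sequence protects the familywise error because a later hypothesis is reached only after every earlier one has been rejected. Here the sequence starts one step too late. H1 and H2 are both tested at 0.05, and neither depends on the other. The trial could miss its primary endpoint and still report MRC, and what follows it, as confirmatory findings under a stated claim of overall error control.

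A second gap is the passing rule. Where a step covers several variables or visits, the protocol does not say whether one significant result opens the next gate or all are needed. The error rate of the step depends on that choice. If it is left open until the data are known, the component that passes can be chosen after the fact.

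**Working it through.** **1. The level implied by the plan.** The protocol gives no familywise figure. With each step at 0.05 and overall control claimed, the implied level is 0.05. Read as five single tests and taken alone, H2 to H8 do have a familywise error of 0.05, because a false claim requires the first true null in the chain to be rejected. The secondary family is consistent on that reading. The problem is its link to H1.

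**2. H1 and H2 both tested at 0.05, no effect on either.**

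- Independent tests: 1 - (1 - 0.05)² = 1 - 0.9025 = 0.0975.
- Correlated normal test statistics, by simulation with assumed correlations:

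| Correlation | P(H1 or H2 falsely rejected) |
|---|---|
| 0.5 | 0.091 |
| 0.7 | 0.083 |
| 0.8 | 0.078 |
| 0.9 | 0.070 |
| 1.0 | 0.050 |

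**3. The same with CRC and MRC taken from one measurement.** CRC is recession depth equal to zero, and MRC is the percentage of baseline recession covered, so both use the same reading. Simulation set-up: 40,000 null trials per setting, 15 per arm, normally distributed coverage with SD 15 percentage points (assumed) capped at 100%, a t-test on MRC, and a common CRC rate between 33% and 80%, the two planning rates of section 5.2.3. The protocol does not name the CRC test, so two were tried:

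- uncorrected chi-square for CRC: H1-or-H2 error about 6-9%;
- Fisher's exact test for CRC: about 3-6%.

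Fisher's test gives less because it is conservative at this sample size.

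**4. False-pass rate of a step if any one component sufficed.** These rates apply given that the earlier steps have passed and that no component of the step in question has an effect. Independent case: 1 - 0.95^k. The lower figure is a simulation with a common correlation of 0.8 (assumed).

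| Step | Tests k | Independent | Correlation 0.8 |
|---|---|---|---|
| H3: CAL, PD | 2 | 9.75% | 7.9% |
| H4: four visits | 4 | 18.5% | 11.4% |
| H5: three scales at one visit | 3 | 14.3% | 9.7% |
| H5: three scales × three visits | 9 | 37.0% | 16.5% |

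If all components must be significant, every one of these steps stays at or below 5%.

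**5. After the correction.** With H1 as the first gate at two-sided 0.05, and each later step held at level 0.05, the sequence H1, H2, H3, H4, H5, H8 has a familywise error of at most 0.05.

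**The case against.** The best defence is that the excess is small and may be absent. CRC and MRC share one measurement, so 9.75% is an upper figure. With Fisher's exact test the union is about 3-6%, and in the shared-measurement simulation wrong claims in the direction of benefit stayed at 4.2% or less in every setting. MRC alone is one test at 0.05, and the primary test is untouched. All of this stands. It limits the size but does not supply the missing link between H1 and H2. Any control would then come from the conservatism of a test that the protocol does not name.

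The passing rule and the visit tested are often left to the SAP, and section 5.1.1.2 is a measurement schedule that does not say every visit is tested. H3 and H5 are worded as conjunctions, so an all-components reading is natural and safe. This is why the bundling is only a secondary point. The missing gate is different: the protocol itself fixes the order, the level and the gate, and claims the control.

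A reader might infer more than the documents support:

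- **That a pain benefit could be falsely confirmed in 17-37% of null trials.** Those rates are conditional on H2 to H4 having passed. With no effect anywhere, the any-component rates under independence give 0.05 × 0.0975 × 0.185 × 0.37 ≈ 0.0003, or 0.03%.
- **That a fixed sequence needs exactly one test per step.** It needs a level-0.05 test per step, and an all-components rule also qualifies.
- **That CRC will very likely miss.** At the planning rates of 80% and 33% with 15 per arm, power is 61% by Fisher's exact test and 76.5% by the pooled formula. A miss is plausible but not the likelier result. Section 5.2.3 already concedes low power for smaller effects.
- **That probing depth must end the chain at H3.** This needs the all-components reading, the opposite of the one that inflates error, and the protocol gives no baseline mean or SD for probing depth.
- **That the null hypothesis wording changes the error rate.** It describes a result and not a treatment effect, which is loose, but no test depends on it. A null restricted to CRC would leave H2 to H8 without one.

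**Conclusion.** The multiplicity rule is wrong as written in one respect: H2 is not gated on H1, so the overall control claimed in section 5.5 is not guaranteed, and MRC could be called confirmatory after CRC fails. This follows from the text and needs no assumption.

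The size does rest on assumptions. It is 9.75% under independence, about 6-9% with an uncorrected chi-square test, and about 3-6% with Fisher's exact test when both outcomes share one reading. An error rate well above 5% is therefore possible but not established.

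The unstated passing rule for H3, H4 and H5 is secondary. It inflates error only if any one component suffices, and only once earlier gates have opened. RecRed is a minor loose end: it belongs to H2 as worded, but is neither named in the sequence nor among the descriptive outcomes. Severity: should fix.

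**What to change.** Amend the Multiplicity Control paragraph of section 4.4.1, before any unblinded data are seen:

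1. State that H1 (CRC at 12 months) is tested first at two-sided 0.05, and H2 onward only if H1 is significant. Otherwise all secondary results are descriptive.
2. For H3, H4 and H5, either name one variable at one time point or state that all components must be significant. For H5, settle first whether the VAS is collected at the section 5.1.1.2 visits or at 1 week as in section 7.6.8.
3. List RecRed either as descriptive or as part of H2.

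The cost is one paragraph, with no change to sample size or data collection. The price is that no confirmatory secondary claim is available if CRC misses. An all-components rule also makes a step harder to pass, most of all for H5 if all nine VAS results count. Section 5.5 can then stand as it is.
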